### 13.1 Recruitment rates

We plan to screen an average of 147 and recruit 37 men per month on average during recruitment with predicted numbers lower in initial, and higher in later phases of recruitment. From CPRD 2014 data we estimate an incidence of four men per practice per month. Target accrual rates are presented in the Figure below:

## 14 Qualitative Data Collection

### 14.1 Internal pilot phase qualitative evaluation

A qualitative evaluation will be included in the internal pilot. The aims of this qualitative evaluation will be to:

- Assess patients' acceptability of the reference urodynamic assessment, identifying barriers / facilitators to the uptake of, or satisfaction with the test
- Understand patients' experiences of lower urinary tract symptoms, their management of the symptoms/condition, their decision to seek medical advice, and the factors that matter most to patients
- Identify other barriers / facilitators to participation in the study (from perspective of both healthcare professionals and patients)
- Identify themes relating to positive and negative experiences of taking part in the study (from perspective of both healthcare professionals and patients)
- Use the results to inform strategies that will maximise recruitment and retention

Semi-structured interviews will be carried out with patients recruited to the main study to gather in-depth information on their experience of participating in the study. We will also interview a sample of patients who declined to participate in the main study. Interviews will also be conducted with healthcare professionals that are involved in recruiting / consulting with patients invited to / taking part in the study. These will be conducted face-to-face or by telephone.

### ***Participants and recruitment***

Qualitative evaluation will be conducted with 12-15 patients who agree to participate in the main study (during the pilot phase). The patient consent form for participation in the main study will include consent to be contacted for the qualitative interview. Patients will be selected to ensure representation from different general practices, across the three study regions (Wales Primary Care Research Network; North East England and North Cumbria Research Network; Western Research Network). The patients selected will be contacted within two weeks following their second research visit (during which they will undergo the reference test - urodynamics), to invite them to take part in an interview. If they agree, they will be sent an interview study patient information sheet and a consent form, which they will need to return to the research team. A convenient time / location will be arranged for the researcher to interview them. We will also conduct qualitative interviews with approximately 5 patients who declined to participate in the main study. Recruiting healthcare professionals will invite these individuals to take part in a short interview study; those who agree will be given an interview study patient information sheet, study reply form, and consent form, which they will return to the research team if they want to participate. A researcher will then contact them to arrange a convenient time / location for an interview.

We will also conduct interviews with 10-15 healthcare professionals (ensuring representation from each study region, to account for local recruitment/study differences). We will write to the participating general practices to inform them about the qualitative pilot work, and to ask them to identify individual healthcare professionals that would be interested in taking part in an interview. We will telephone the practices to obtain a list of interested individuals. We will then contact the healthcare professionals directly to arrange a convenient time and location for the interview (anticipate that these interviews will take place towards the end of the pilot-phase to allow sufficient experience of recruiting patients). Written consent will be obtained for face-to-face interviews. Consent will be given verbally for telephone interviews (verbal consent will be audio recorded).

### ***Data collection and analysis***

A trained qualitative researcher will conduct the interviews. Prior to conducting the interviews, the researcher will make sure that consent (written or verbal consent) has been received, and they will briefly outline what the interviews will involve. All the interviews will be audio-recorded and transcribed verbatim. The qualitative researcher conducting the telephone interviews will also ensure that verbal consent is audio-recorded. It is anticipated that the interviews will last approximately 30-45 minutes. The interviewer will use a flexible semi-structured interview guide to ensure the essential

information is gathered, whilst allowing the interviewer flexibility to explore emerging themes. Broadly, interviews will assess practicality and acceptability of conducting urodynamics.

The patient interview guide will explore patients' reactions to the test (e.g. How did you feel about having the test? What was your experience of that test? Did you have any concerns? Was it better/worse than anticipated? Were there any problems/delays? Did you think it was useful? How might the process be improved?), and also their experience of the recruitment and study process (e.g. How were you asked to take part in the study? Do you think you were given the right information about urodynamics beforehand? Was there anything that might put people off taking part?). The interview guide will also explore the patient's experience of having LUTS and of managing their symptoms / condition, the factors influencing their decision to seek medical advice, and the factors that matter most to them when managing the symptoms or making a decision about the management of the condition.

The clinician interview guide will explore the general practitioners' experiences of the study recruitment process (e.g. any difficulties experienced approaching the discussion of having urodynamics), and also insights into their patients' responses to the process and the urodynamic assessment (if known, e.g. a patient might have discussed their concerns about the urodynamic assessment with their general practitioner).

Interview transcripts will be analysed thematically using NVivo qualitative analysis software. A coding framework will be developed based on the pre-defined themes included in the topic guide, and new themes emerging from the data. In-depth qualitative research during the pilot phase will allow us to identify problems that might undermine the acceptability of the study, particularly undertaking urodynamic tests, and to develop strategies that will maximise recruitment and retention. It will also provide us with a more detailed understanding of how the men experience the symptoms / management of LUTS, and the factors that matter to them as patients with this condition.

## **14.2 Development of Management recommendations**

A group of 20-25 stakeholders will attend a consensus meeting during Autumn 2017. This will include urologists, GPs and men with LUTS either as separate groups or in a plenary. The co-applicants from these stakeholder sections (urology, PPI, primary care) will undertake to invite and recruit these members, and we will liaise closely with patient representative groups. The participating clinicians will be presented with a number of clinical case scenarios ( $n \approx 16$ ), where they will be asked to consider

how they could be managed (using standard RAND methodology). Group facilitation and the methods used to elicit opinions on treatment management will be carefully planned to ensure that the opinions of all of the stakeholders are elicited, and considered. This group will also be contacted at times during the study for comment, interpretation of preliminary conclusions, and for input into aspects of the management recommendations etc. In this way the group will be informed about study progress, and be able to provide further feedback, thus operating as a “Reference Group”. We propose also to re-convene the Consensus / Reference group towards the end of the data interpretation phase (including the assessment of qualitative data about feasibility and likely implementation) for additional feedback, and to contribute to planning of a subsequent implementation / evaluation study application. The later meeting will also examine potential for early impact from the findings as they stand, with publicity to patients, patient groups, GPs, other staff, and management / commissioning groups where actionable findings are evident. Throughout the process we will take specific steps to support the patient and PPI representatives to feel confident to contribute.

### **14.3 Tool usability and acceptability**

Interviews will be conducted with GPs who will be the main clinician group using the decision aid to inform management discussions with their patients. We aim to recruit a total of 30 general practitioners across the three study hubs (ten interviews per hub). We plan to use a ‘think aloud’ protocol and a semi-structured interview guide to initially explore clinicians’ opinions on the optimum characteristics of the design aid, its potential use in routine practice over a number of different diagnostic scenarios and in the later stages of the study, their reactions to the prototype decision aid. The ‘think-aloud’ method is commonly used for usability testing, and involves participants thinking aloud as they perform a task [8]. ‘Think-aloud’ verbalisations will be audio-recorded and transcribed for analysis. The clinicians will then take part in a short semi-structured interview (30-60 minutes). The interview guide will cover the following topics (expanding on topics already discussed during the ‘think-aloud’ protocol): diagnostic aid design; user-friendliness; use with patients; fit of inputs and outputs with local clinical systems (including information technology systems); potential influence on clinicians’ behaviour (i.e. decision making and setting of diagnostic accuracy thresholds); problems encountered/perceived; unexpected consequences; perceived benefits of decision aid; contextual factors that might impact use or future implementation. Interviews will also be conducted with a sample of patients participating in the study. We aim to conduct 30 patient interviews (ten interviews per hub) between 2-4 weeks after their initial management has been decided. These patients will be presented with a prototype example of the diagnostic decision aid and will be told how it will be used to inform the management discussion with a GP. The standard care pathway will also be presented to patients as a comparison to the proposed alternative pathway, which will include locality of care and

average wait times. Using these hypothetical scenarios, we will conduct semi-structured interviews to assess potential acceptability to patients, and feasibility of introducing the decision aid into primary care.

#### **14.4 Referral Rates**

We will ascertain the number of men recommended for referral by GPs who used the output of the prediction model and considered the management options recommended and compare this with 5-year data from the Clinical Practice Research Datalink (CPRD; historical control) to estimate potential impact of the aid on referral rates. The CPRD holds anonymised primary care records from almost 700 practices across the UK and by July 2013 had abstracted data from primary care records stored by a variety of bespoke GP systems for almost 12 million patients with median follow-up of 5.1 years and [9]. The CPRD has previously been used to define cohorts of men with benign prostatic hypertrophy for epidemiological studies [10, 11]. We will use the CPRD to estimate recent trends in referral rates for men presenting to UK primary care with an incident episode of LUTS. For these historical control data, our denominator will consist of men aged 16 and over whose primary care records contain a Read code indicating an incident presentation with LUTS. We will define incident presentations as those without a prescription for an alpha-blocker (except doxazosin), 5-alpha reductase inhibitor or combination drug at the time of incident presentation and without a LUTS related Read code in the preceding 365 days. Where doxazosin is prescribed, we will only include men who have a Read code for hypertension and no prior record of LUTS. To include only probable benign cases, we will exclude men with a Read code suggesting a urological malignancy, haematuria, urinary tract infection or a prostate specific antigen above the age-specific reference range within 28 days after incident LUTS presentation. Our numerator will consist of men from our denominator whose primary care records contain a Read code indicating referral to specialist urology services within 28 days of the incident LUTS presentation. This short time period is to increase likelihood that referral is due to initial presentation and not to treatment failure. We will describe referral rates over time and by age-group and compare these with the referral rate occurring during practice participation in the PriMUS study to understand the potential impact of widespread use of the aid on secondary care services. We will specify the assumption that this referral rate reflects decisions based on the reference standard urodynamic result, and will model variations on this according to the observed accuracy of the decision aid in the validation study.

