## 2 Synopsis

Short title	Primary care M anagement of lower U rinary tract S ymptoms in men: Development and validation of a diagnostic and decision-making aid.
Acronym	PriMUS
Internal ref. no.	388
Funder and ref.	NIHR Health Technology Assessment (HTA) 15/40/05
Study design	Diagnostic Accuracy Study
Study setting	Primary Care and the Community
Study participants	Men consulting their GP with Lower Urinary Tract Symptoms (LUTS)
Planned sample size	880
Inclusion criteria	
 
• Men aged 16 years and over.
 
• Men who present to their GP with a complaint of one or more bothersome lower urinary tract symptoms (LUTS)#
 
• Men able and willing to give informed consent for participation in study
 
• Men able and willing to undergo all index tests and reference test, and complete study documentation.
 
 
# This would include men on current treatment, but who are still symptomatic

Exclusion criteria	
 
• Men with neurological disease or injury affecting lower urinary tract function
 
• Men with LUTS considered secondary to current or past invasive treatment or radiotherapy for pelvic disease
 
• Men with other contraindications to urodynamics e.g. Heart valve or joint replacement surgery within the last 3 months, immunocompromised/immunosuppressed.
 
• Men with indwelling urinary catheters or who carry out intermittent self-catheterisation
 
• Men whose initial assessment suggests that clinical findings are suggestive of possible: 
 
○ prostate or bladder cancer*
 
○ recurrent or persistent symptomatic UTI**
 
○ renal impairment
 
○ retention
 
 
 
• Men unable to consent in English or Welsh where a suitable translator is not available. This is a multi-centre study based in primary care, and we cannot guarantee translation facilities at all sites
 
 
*According to standard NHS cancer pathways. If later deemed unlikely, then eligible for study participation.
 
**If UTI successfully treated but LUTS remain, then eligible for study.

Recruitment duration	24 months
Follow-up duration	6 months
Planned study period	1 st May 2017 – 30 th April 2020

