### 3.2 Study Schema

## 4 Background

The syndrome of lower urinary tract symptoms (LUTS) occurs mostly in older men and is a bothersome condition detrimental to quality of life (QoL). It can usually be managed without invasive treatment and is very rarely a threat to life or long term health. Male LUTS accounts for four presentations each month in an average sized GP practice (CPRD, 2014). This rate of presentation makes it difficult for GPs to gain sufficient expertise to be confident about diagnosis and management. Consequently, men are frequently referred to urology specialists who often recommend treatments that could have been initiated in primary care. Clinical uncertainty also leads to variation in referral patterns between individual GPs, practices and localities. To address this, the National Institute for Health and Care Excellence (NICE) issued guidance for Male LUTS in 2010 (revised 2015) mapping out initial assessment and conservative management within primary care [1]. Despite this the proportion of men referred to urology services following an incident presentation of LUTS rose from 10% in 2009 to 30% in 2013 (CPRD 2014) at an approximate extra cost to NHS England of £2 million. Implementation projects commissioned by the NHS concluded that further support with access to simple accurate tests, diagnostic protocols and decision aids was needed to facilitate patient management in primary care and ensure best value for patients and the NHS from specialist referral [2].

One of the difficulties faced in primary care is obtaining and interpreting simple clinical measurements that differentiate causes of male LUTS and hence guide effective symptom management. The underlying conditions that disturb lower urinary tract function, with their approximate prevalence are: detrusor overactivity (57%), bladder outlet obstruction (31%), and detrusor underactivity (16%). The diagnoses may appear individually or in combination. An additional contribution to male LUTS arises from ageing-related changes in fluid homeostasis which commonly result in nocturnal polyuria (30%) diagnosed from a 24-hour record of urine output. Nocturnal polyuria, although not a urodynamic abnormality, must be considered when making a diagnosis in men with nocturia as a prominent symptom. About a third of men with LUTS have a combination of two or more underlying causes [3, 4].

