#### **4.1 Rationale for current study**

##### **Why is the research important in terms of improving the health of the public and/or to patients and the NHS?**

Male LUTS is rarely a threat to life or health but patients often find the problem very intrusive to work and social life. The current concentration of diagnostic assessment and initiation of treatment in secondary care usually means a delay in addressing the problem, and inconvenience and extra embarrassment at having to have hospital assessment at a distance from home. A primary care-based decision aid with defined accuracy would firstly mean that the men could undergo the necessary simple tests straightaway organised through the GP surgery and secondly would get a much timelier result regarding predicted diagnosis and choice of management options that are most likely to be effective. For GPs the aid would allay uncertainty around both diagnosis and best management. Specialist urology units would concentrate more on specialist investigation and treating the 10-20% of men who require complex management such as surgery. Those men still requiring early referral or who have not benefitted from simple management options would be referred with a much more informed perspective of their problem with all the initial diagnostics completed making planning of further care quicker and seamless. Reducing rates of referral to secondary care for a number of clinical conditions has been identified as one way of improving delivery of NHS care. Full economic evaluation is not included in this study since the design concentrates on diagnostic accuracy. However, using the rate of consultation and referral documented in the CPRD, we estimate that, if referrals to secondary

care were halved, the NHS in England would be saved about £1.3 million per year from reduced out-patient attendance. Although such a change would require one extra 15-minute consultation with the GP, the relatively low prevalence of the condition means this should not noticeably impact on GP workload. Assessment and initial treatment costs would be unchanged but will be incurred in the primary rather than secondary care setting. Outcome from the patient perspective should not change since GPs will now be receiving the same treatment recommendation from the decision aid that they would have previously been sent from the secondary care urology clinic.

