### **5.4 Secondary Outcome Measures**

- Construction of a patient management algorithm to guide initial treatment for men with LUTS
- Construction of a prototype online decision aid for use in primary care
- Qualitative analysis of patients and clinicians views on the use of a LUTS decision aid in the primary care setting
- Percentage change in referral rates to secondary care for men with LUTS

- Estimation of costs / savings of implementation of the primary care LUTS decision aid both from a population and individual patient perspective.

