## **17.4 Other Analyses**

### **17.4.1 Referral rates**

The potential impact of the decision aid on referral rates will be calculated by expressing the difference between rates occurring during GP practice participation in the PriMUS study including consideration of urodynamic diagnoses provided by use of the reference test with the historical control of practices participating in the CPRD data collection.

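### The change in referral rate is measured against an undated 5-year CPRD historical control without removing calendar trend, although the Background reports a steep rise in that rate

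*Protocol*

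**What the plan says.** Section 5.4 lists as a secondary outcome "Percentage change in referral rates to secondary care for men with LUTS". Section 14.4 sets the comparator: the study will "compare this with 5-year data from the Clinical Practice Research Datalink (CPRD; historical control) to estimate potential impact of the aid on referral rates". Section 17.4.1 sets the estimator. The impact is "calculated by expressing the difference between rates occurring during GP practice participation in the PriMUS study", and the other side of the difference is described as "with the historical control of practices participating in the CPRD data collection". Neither section gives the calendar years of the five-year window.

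The Background (section 4) says that the proportion of men referred to urology after an incident presentation "rose from 10% in 2009 to 30% in 2013 (CPRD 2014". According to the Synopsis, the study runs from 1 May 2017 to 30 April 2020, with 24 months of recruitment and 6 months of follow-up.

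Section 14.4 also says "We will use the CPRD to estimate recent trends in referral rates for men presenting to UK primary care", and that rates over time and by age group will be set beside the study rate. The only variation it plans to model is the accuracy of the decision aid. Calendar time is not mentioned there.

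**The concern.** A control from earlier years stands in for what would have happened in the study years without the aid. That needs either a stable rate or a correction for its movement. By the Protocol's own figures the rate was not stable: it tripled in four years. If it kept moving after 2013, the difference in section 17.4.1 mixes the effect of better diagnostic information with the passage of time. A continuing rise would hide part or all of a real reduction, and a fall would create an apparent one.

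This is separate from any difference in case definition or observation window between CPRD and the study. It would remain if those were made identical.

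**Working it through.** **The Protocol's own figure.** 30% / 10% = 3.0 over 2009-2013. If linear, (30 − 10) / 4 = 5 points a year. The Protocol states no sample size, power or margin for the referral comparison, so there is no planned figure to reproduce.

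**Timing (assumed).** Six months of set-up (section 26) from May 2017, then 24 months of recruitment (Synopsis), puts recruitment at November 2017 to October 2019, midpoint about November 2018. With 6 months of follow-up this fills the 36-month study period. The milestone list in section 26 is shorter, so these dates remain an assumption. Five years directly before recruitment would be November 2012 to October 2017, midpoint about May 2015. The gap between midpoints is 3.5 years.

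**Formula.** If the five years are averaged (also an assumption) and the trend is linear, then with no effect of the aid:

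bias = slope per year × 3.5 years.

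In calendar years, take the control as 2013-2017 and the study as the mean of 2018 and 2019. This again gives a 3.5-year gap. The last control year, 2017, lies 1.5 years before the study midpoint. Every trend after 2013 in this table is assumed, starting from 30% in 2013:

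| Assumed trend after 2013 | Mean 2013-2017 | 2017 | Study rate, no effect | Bias against 5-year mean | Bias against 2017 alone |
|---|---|---|---|---|---|
| Flat | 30% | 30% | 30% | 0 | 0 |
| +1 point a year | 32% | 34% | 35.5% | +3.5 | +1.5 |
| +2.5 points a year | 35% | 40% | 43.75% | +8.75 | +3.75 |
| +5 points a year | 40% | 50% | 57.5% | +17.5 | +7.5 |
| −5 points a year to 10% in 2017, then flat | 20% | 10% | 10% | −10 | 0 |

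**Against sampling error.** The 95% half-width for a 30% rate is 1.96 × √(0.3 × 0.7 / n). This is 3.0 points at n = 880 and 3.5 points at n = 675. A drift of 1 point a year is therefore already about as large as the sampling uncertainty.

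**Effect on a real reduction.** Section 4.1 uses halved referrals as its illustration. Measured against the 5-year mean, a true 50% reduction would show as:
- flat: 15 against 30, −50%;
- +1 point a year: 17.75 against 32, −45%;
- +2.5 points a year: 21.9 against 35, −38%;
- +5 points a year: 28.75 against 40, −28%.

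The sign stays right in these cases. It turns only when the true relative reduction is smaller than drift / study-period rate: 3.5 / 35.5 = 10%, 8.75 / 43.75 = 20%, and 17.5 / 57.5 = 30% for the three rising trends.

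**The case against.** The strongest reply is that the Protocol is not blind to trend. Section 14.4 will estimate recent trends and compare rates over time with the study rate, so yearly figures will be at hand. This stands, and it narrows the point: the gap is that section 17.4.1 does not carry those trends into the difference.

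A reader might infer that the Protocol pools the five years into one average. It does not say so; averaging is an assumption in the working above. A comparison with the last pre-study year would have a smaller bias (0 to 7.5 points under the flat and rising trends), though not zero if the rise continued.

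A reader might also take 17.5 points as the expected bias. That figure needs a usual-care referral rate of 57.5% by 2018-2019, and nothing in the Protocol supports that. Likewise, one can build a sign change from a 2009-2013 window: a hypothetical study rate of 25% is +25% against a mean of 20% but −17% against 30%. The Protocol does not say that the control covers those years.

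Finally, extract dates and trend adjustment are often left to the analysis plan, which is not shown. But the Protocol itself fixes the type of control, its length and the difference estimator. An analysis plan also cannot recover calendar months that were never extracted.

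**Conclusion.** The concern holds as a possible bias of unknown size in one secondary outcome. The Protocol documents a strongly moving rate, names a historical control without dates, and defines the effect as a difference from it without a concurrent comparator or a trend correction.

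For a rate that is level or rising, with a window directly preceding recruitment and averaged years, the bias ranges from 0 (plateau before the window) through about 3.5 points (1 point a year) to 17.5 points (only if the 2009-2013 slope continued). A fall after 2013 would bias in the other direction. The Protocol gives no rate after 2013 with which to choose among these.

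Two further inferences are not supported. The cost comparison in section 17.3 may look as though it inherits the error, but that section does not name the CPRD difference as an input. Nor does the point touch the sensitivity and specificity outcomes or the sample size, which do not depend on referral. The referral result is worded as an estimate of potential impact, with no hypothesis test attached, so this is an inexpensive improvement and not a threat to the study.

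**What to change.** In sections 14.4 and 17.4.1, make the main comparator the CPRD referral rate for the same calendar months as PriMUS recruitment, from an extract cut after recruitment closes. Name the calendar years of the preceding five-year period and use it to describe the trend.

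If a concurrent extract cannot be had in time, compare the study rate with the rate projected to the study period from the yearly CPRD rates, and report its prediction interval. State that a multi-year average is not the comparator. The projection would rest on about five yearly points, so it is the second choice.

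The cost is a change of extract dates and a few sentences in the two sections. The extract comes later, and a comparator of about two years is slightly less precise than one of five. With almost 700 practices in CPRD (section 14.4), that loss should be negligible.
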